# 12.2.2 Observational Component

The following will be analysed for patients in the observational component:

- The outcome and treatment of this patient group
- Quality of life as measured by the MPN SAF; EQ-5D-5L and EORTC QLQ-C30 at registration, 3 months and 6 months

# 12.2.3 Exploratory

The following will be analysed for all patients contributing to samples for in the interventional and observational component:

• Change in clonal marker (e.g., JAK2 or CALR allele burden) from baseline to end of cycles 3 and 6 (samples taken on day 22-25 of cycle 3 and cycle 6)

# **12.3 Analysis of Outcome Measures**

Descriptive statistics will be reported for all patients recruited as described below.

#### Interventional component

Primary outcome measure

• The MTD, defined as the dose level with an associated DLT probability over the first cycle of treatment (28 days) closest to the target DLT rate of 25%, will be reported with its associated probability of DLT and 90% probability interval.

Secondary outcome measures

- Best response following 3 and 6 cycles of treatment will be reported as the number and proportion of patients in each response category and overall.
- DLTs and AEs (according to the CTCAE criteria version 4.0), records of blood and platelet transfusions, physical examinations to assess spleen and liver size, blood counts (including haemoglobin and platelet count, quality of life questionnaires and survival data) will be collected and reported in a descriptive manner.

# **Observational component**

The analysis cohort will be all patients registered to this part of the trial.

No formal hypothesis testing is planned for the study. All analysis will be in the form of descriptive statistics only, with 95% Confidence Intervals given where appropriate.

# 12.4 Planned Analyses

An interim assessment by the TMG and TSC committees will take place after approximately 24-28 patients are recruited taking into account all safety and activity data available to decide if the CRM model is allowed to continue dose-recommendation until recruitment is completed or if the MTD should be declared earlier and the remaining patients recruited at the declared MTD.

The final analysis of the primary outcome will be performed when the MTD is determined according to the CRM or the maximum sample size is reached.

The final analysis of secondary and exploratory outcome measures is planned for one year after the final patient has enrolled on the study; this will allow enough time for the patient to receive all cycles of treatment and for data to be returned to the trials office.

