# **Trial Duration**

All patients on the interventional component will receive a minimum of 6 cycles of treatment and will be followed up for a further 6 months (total of 12 months from registration). Patients will continue therapy if they receive a clinical benefit at the discretion of the CI.

Patients on the observational component will be assessed over a 6 month period and will be followed up for survival data for a minimum of 1 year from the date of registration.

Recruitment will be over 36 months. Therefore the total trial duration will be 48 months.

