1. Every effort should be made for patients to attend on the scheduled visit days. However, if a patient is unable to attend on the specified day, assessments may be scheduled for +/- 3 days

2. The physical examination and peripheral blood smear may be performed from day 22 of the preceding cycle to the start of the next cycle at local discretion

- 3. Women of child bearing potential only
- 4. Or earlier when there is evidence of remission or progression in the peripheral blood
- 5. Research samples should be taken between days 22-25 (or on a Monday Thursday at baseline) so that they can be received by the biobank. Both research samples (bone marrow and blood samples) should be collected on the same day
- 6. For patients continuing trial treatment beyond cycle 6, bone marrow aspirate, trephine and disease assessments are recommended every 3 months and at progression/relapse. Patients will have a final disease assessment when the additional treatment stops using the information of the most recent previous bone marrow obtained
- 7. The haematology and biochemistry assessments can be performed between days 22-25 to coincide with the collection of research blood and bone marrow samples or safety bloods
- 8. Dose modifications permitted in accordance with section 7.8 of the protocol after cycle 1
- 9. Administered at Chief Investigator's discretion following 6 cycles of combination treatment if patient obtaining clinical benefit
- 10. Patients will be followed up for a minimum of 12 months from study entry for survival and outcome data

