# 7.12 Patient Follow Up

#### Interventional Component

Patients who are gaining clinical benefit at the end of 6 cycles may continue to receive therapy with 5azacitidine and/or ruxolitinib at the discretion of the CI until loss of response or unacceptable toxicity. Patients that have to discontinue the combination therapy due to a toxicity that is clearly related to just one of the trial treatments may continue to take the alternative medication as long as they continue to obtain a clinical benefit in the view of the local investigator and the Chief Investigator (section 7.8.1). Patients will be followed-up for survival data for a minimum of 1 year from the date of start of treatment.

All patients must have a final assessment 28 days after the last dose of trial medication.

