# **11. END OF TRIAL DEFINITION**

The end of trial will be 6 months after the last data capture. This will allow sufficient time for the completion of protocol procedures, data collection and data input. The Trials Office will notify the MHRA and main REC that the trial has ended and will provide them with a summary of the clinical trial report within 12 months of the end of trial.

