#### 12.2.1.2 Secondary outcome measures

The following will be analysed for patients in the interventional component:

- Best response following 3 and 6 cycles of treatment. Response will be assessed according to the following criteria:
  - Proposed criteria for response assessment in patients treated in clinical trials for MPNs in blast phase (MPN-BP): Formal recommendations from the post-MPN acute myeloid leukaemia consortium" (for patients with ≥20% bone marrow blasts at baseline)[1]
  - International Working Group (IWG) response criteria in myelodysplasia (for patients with <20% bone marrow blasts at baseline)[2]

In order to assess disease response, bone marrow, peripheral blood and spleen/liver assessments should be performed during days 22-25 of cycle 3 and cycle 6.

• Achievement of RBC transfusion independence after completion of cycles 3 and 6 compared to baseline.

RBC transfusion dependence is defined as transfusion of  $\geq 2$  RBC units in the 8 weeks prior to registration at baseline, and as transfusion of  $\geq 2$  RBC units in the 8 weeks prior to cycle 3-day 28 or cycle 6-day 28 for subsequent assessments.

• Achievement of platelet transfusion independence after completion of cycles 3 and 6 compared to baseline.

Platelet transfusion dependence is defined as transfusion of  $\geq 1$  platelet units in the 4 weeks prior to registration at baseline, and as transfusion of  $\geq 1$  platelet units in the 4 weeks prior to cycle 3-day 28 or cycle 6-day 28 for subsequent assessments.

- Change in the proportion of RBC or platelet transfusion-dependent patients after completion of cycles 3 and 6 compared to baseline as defined above.
- Change in palpable splenomegaly or hepatomegaly after completion of cycles 3 and 6 compared to baseline

Size of palpable spleens will be measured below the left costal margin and reported in cm Size of palpable livers will be measured below the right costal margin and reported in cm

- Duration of Complete Response (CR) or Partial Response (PR) according to established criteria
   [1] [2]
- 12 months Progression-free survival (PFS)
- 12 months Leukaemia-free survival (LFS)

- 12 months Overall survival (OS)
- Duration of trial treatment
- Mean change in haemoglobin level from baseline to end of cycles 3 and 6 (cycle 3-day 22-25 or cycle 6-day 22-25)
- Mean change in platelet count from baseline to end of cycles 3 and 6 6 (cycle 3-day 22-25 or cycle 6-day 22-25)

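### The secondary analysis, planned for one year after the last enrolment, leaves no time to collect the last patients' 12-month outcomes; separately, the 48-month trial duration contradicts the end-of-trial definition

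*Protocol*

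**What the plan says.** **Timing of the secondary analysis.** Protocol section 12.4 gives the primary outcome its own trigger. The final analysis of secondary and exploratory outcomes is "planned for one year after the final patient has enrolled on the study; this will allow enough time". The reason it gives has two parts: completion of the treatment cycles, and return of the data.

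**What has to be ready by then.** Section 12.2.1.2 lists 12-month progression-free, leukaemia-free and overall survival for the interventional component. For the observational component, sections 7.4 and 7.6 schedule disease assessment, treatment information and blood counts at month 12.

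**How follow-up is counted.**
- The synopsis (Trial Duration) counts 12 months from registration for the interventional component. For the observational component, the synopsis and section 7.12 count at least a year from registration.
- Footnote 10 of the interventional schedule says: "Patients will be followed up for a minimum of 12 months from study entry for survival and outcome data".
- Section 7.12, for the interventional component, says: "Patients will be followed-up for survival data for a minimum of 1 year from the date of start of treatment".

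**Length of the trial.** The synopsis says: "Recruitment will be over 36 months. Therefore the total trial duration will be 48 months". Section 11 says: "The end of trial will be 6 months after the last data capture", to leave room for finishing procedures and for collecting and entering data.

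**The concern.** Section 12.4 asserts that one year is enough and gives its reason, but the reason looks only at the treatment cycles. The longest outcomes in the secondary list need a full year of follow-up, and the analysis is placed one year after the last enrolment. The last patients' 12-month data would have to be observed, recorded, returned and checked within no time at all.

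At stake are complete 12-month rates for the most recently enrolled patients, in a small study where each interventional patient is about 3% of the total (1/34). If the analysis goes ahead on the planned date, those patients are censored a little short of 12 months, or their status is missing.

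The stated duration is a related but separate matter. The synopsis total stops at the last patient's 12-month date, while section 11 keeps the trial open for six months after data capture ends. Both cannot be right.

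**Working it through.** **Inputs from the protocol.** Recruitment 36 months and stated duration 48 months (synopsis); 34 interventional and up to 30 observational patients (synopsis, section 12.1); six cycles of 28 days (section 3.1); cycle delays of up to 4 weeks, with discontinuation after three successive delays (section 7.8.2); final visit 28 days after last dose (section 7.12); end of trial 6 months after last data capture (section 11).

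**Inputs the protocol does not give, so assumed.** Uniform accrual; a data-return lag of 1 to 3 months; a gap of 7 to 28 days from registration to first dose. Enrolment in section 12.4 is read as registration.

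**Step 1: reproduce the stated duration.** 36 + 12 = 48 months, as stated. This ends on the last patient's 12-month date, with nothing after it.

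**Step 2: check the reason in section 12.4.** Six cycles take 6 × 28 = 168 days. Cycles 2 to 6 have five start dates; with no three successive delays, at most four can be delayed: 168 + 4 × 28 = 280 days. Adding the final visit gives 280 + 28 = 308 days, which is inside 365. The reason holds for treatment, but says nothing about outcomes due at day 365.

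**Step 3: follow-up of the last patient on the planned date.**
- From registration: 365 of 365 days elapsed, so 0 days remain for data return.
- From start of treatment: 365 minus the gap. For gaps of 7, 14 and 28 days this is 358, 351 and 337 days, so month 12 has not been reached.

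**Step 4: how many patients.** Number affected = accrual rate × lag.
- Interventional, 34/36 = 0.94 per month: lags of 1, 2 and 3 months give 0.9, 1.9 and 2.8 patients (3%, 6%, 8% of 34).
- Observational, 30/36 = 0.83 per month: the same lags give 0.8, 1.7 and 2.5 patients (3%, 6%, 8% of 30).

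**Step 5: allow for patients whose outcome is already known.** A patient who died before the data cut has a known overall survival outcome, and one who progressed has a known progression-free outcome. Only patients event-free at their last return are open. Section 1.1 cites a median survival of 6 months in blast phase. With exponential survival (assumed), 28% are alive at month 11 and 35% at month 9. For overall survival the open number is then at most about 0.94 × 0.28 = 0.3 patients for a 1-month lag and 2.83 × 0.35 = 1.0 for a 3-month lag. If 50% were alive, since accelerated-phase patients may do better, it is 0.94 × 0.5 = 0.5 to 2.83 × 0.5 = 1.4.

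**Step 6: duration under section 11.** If recruitment takes the full 36 months, last data capture is no earlier than month 36 + 12 = 48. The trial then ends at 48 + 6 = 54 months at the earliest. Treatment may continue past cycle 6 with no stated limit, so 54 is a minimum.

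**The case against.** The strongest reply is that these are small mismatches. Section 12.4 says the date is planned, not fixed, and covers only secondary and exploratory outcomes, which section 12.3 reports descriptively. On the registration clock every patient has a full year of elapsed follow-up on the analysis date, so only data return is short. If the last enrolment is observational, the interventional data will have extra time. All of this stands. It limits the size of the problem, but section 12.4 still claims time for data return that it does not provide at month 12.

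A reader might infer more than the documents support:

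- *That three time origins shift every 12-month rate.* Section 6, on trial entry, describes registration, and section 7.1 separates study entry from day 1 of cycle 1. Study entry is therefore in effect registration, and there are two clocks. Both set lengths of follow-up. Neither defines the origin of an endpoint, which may be left to the SAP.
- *That the 6 months in section 11 is a reporting lag, leaving 17% of patients (5.7 of 34) or half of an MTD group without 12-month status.* Section 11 counts from last data capture to end of trial. It gives no per-patient lag before analysis. The 12 patients in section 12.1 are those already at the MTD when early declaration is allowed, so later recruits would add to that number.
- *That the loss falls mainly at the recommended dose.* This is plausible, because late cohorts follow the model's recommendation or the declared MTD, but it is an inference. The protocol does not state it.
- *That the 48-month figure fails for the same reason as the analysis date.* It conflicts with section 11, a different rule.

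**Conclusion.** The point holds in limited form. The analysis date in section 12.4 coincides with the last patient's 12-month date on the registration clock. It precedes that date on the start-of-treatment clock in section 7.12 unless treatment begins on the day of registration. Its claim of enough time for data return fails for the 12-month outcomes.

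The size is modest: at most about 1 to 3 of 34 interventional patients (3 to 8%), and about 0.3 to 1.4 for overall survival once earlier deaths are allowed for. These figures rest on uniform accrual, a 1 to 3 month lag and the survival fractions in the working, all assumed. The MTD analysis is not touched.

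The duration conflict needs no assumption about lag. If recruitment takes the planned 36 months, the synopsis and section 11 differ by at least 6 months (48 against at least 54).

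**What to change.** 1. **Section 12.4.** Replace the fixed year with a trigger: the secondary and exploratory analysis takes place once the last patient in either component has reached 12 months from registration and the 12-month data have been returned. State the period allowed for that return. Three months would be one choice, giving 15 months after last enrolment; the protocol offers no figure, so this is an assumption for the trial team to settle.
2. **Section 7.12, interventional component.** Count follow-up from registration, to match the synopsis, and say in footnote 10 (both copies of the schedule) that study entry means registration.
3. **Synopsis, Trial Duration.** Restate the total as at least 54 months, in line with section 11.

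The cost is protocol wording and secondary results a few months later. The primary analysis keeps its own timing.

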# 13. TRIAL ORGANISATIONAL STRUCTURE

# 13.1 Sponsor

The trial is sponsored by the University of Birmingham.

# **13.2 Coordinating Centre**

The trial is being conducted under the auspices of the Cancer Research UK Clinical Trials Unit (CRCTU), University of Birmingham according to their local procedures.

# 13.3 Trial Management Group

The Trial Management Group (TMG) will consist of the Chief Investigator, Clinical coordinator, Statistical Consultant and the trials team at the CRCTU. The TMG will provide overall supervision of the trial; in particular clinical set-up, ongoing management, adherence to the protocol, consideration of new information and interpretation of the results. The TMG will meet every three months. An emergency meeting may be convened if a significant issue is identified.

# **13.4 Trial Steering Committee**

A TSC will provide overall supervision for the trial and provide advice through its independent chair. The ultimate decision for the continuation of the trial lies with the TSC. The TSC will meet once each cohort of patients completes the first cycle of their combined treatment, or more often if required, to perform a formal assessment of DLT.

In each meeting, the TSC will be presented with recruitment and safety data. During the second stage, a statistical report for next dose recommendation will also be provided, and the TSC will decide whether to progress to the recommended dose as indicated by the CRM model.

If no DLTs have occurred, the TSC may review the data via correspondence.

# 13.5 Finance

This is a clinician-initiated and clinician-led trial funded by the Bloodwise Trials Acceleration Programme (TAP). Additional funding from Novartis Ltd and Celgene Ltd has also been provided for the management of the trial. Ruxolitinib and 5-azacitidine have been provided free of charge by Novartis Ltd and Celgene UK Ltd respectively.

No individual per patient payment will be made to NHS Trusts, Investigators or patients. This trial has been adopted into the NIHR CRN Portfolio.

# **14. ETHICAL CONSIDERATIONS**

The trial will be performed in accordance with the recommendations guiding physicians in biomedical research involving human subjects, adopted by the 18th World Medical Association General Assembly, Helsinki, Finland, June 1964, amended at the 48th World Medical Association General Assembly, Somerset West, Republic of South Africa, October 1996 (website: http://www.wma.net/en/30publications/10policies/b3/index.html).

The trial will be conducted in accordance with the Research Governance Framework for Health and Social Care, the applicable UK Statutory Instruments, (which include the Medicines for Human Use Clinical Trials 2004 and subsequent amendments and the General Data Protection Regulation and the Data Protection Act (2018) and Human Tissue Act 2008) and Good Clinical Practice (GCP). This trial will be carried out under a Clinical Trial Authorisation in accordance with the Medicines for Human Use Clinical Trials regulations. The protocol will be submitted to and approved by the main REC prior to circulation.

Before any patients are enrolled into the trial, the Principal Investigator at each site is required to obtain local R&D approval. Sites will not be permitted to enrol patients until written confirmation of R&D approval is received by the Trials Office.

It is the responsibility of the Principal Investigator to ensure that all subsequent amendments gain the necessary local approval. This does not affect the individual clinicians' responsibility to take immediate action if thought necessary to protect the health and interest of individual patients.

# **15. CONFIDENTIALITY AND DATA PROTECTION**

Personal data recorded on all documents will be regarded as strictly confidential and will be handled and stored in accordance with the General Data Protection Regulation and the Data Protection Act (2018). With the patient's consent, their full name and date of birth will be collected at trial entry. Patients will be identified using only their unique trial number, initials, and date of birth on the Case Report Form and correspondence between the Trials Office and the participating site. However patients are asked to give permission for the Trials Office to be sent a copy of their signed Informed Consent Form which will not be anonymised. This will be used to perform in-house monitoring of the consent process.

The Investigator must maintain documents not for submission to the Trials Office (e.g. Patient Identification Logs) in strict confidence. In the case of specific issues and/or queries from the regulatory authorities, it will be necessary to have access to the complete trial records, provided that patient confidentiality is protected.

The Trials Office will maintain the confidentiality of all patients' data and will not disclose information by which patients may be identified to any third party other than those directly involved in the treatment of the patient and organisations for which the patient has given explicit consent for data transfer. Representatives of the PHAZAR trial team may be required to have access to patient's notes for quality assurance purposes but patients should be reassured that their confidentiality will be respected at all times.

# **16. INSURANCE AND INDEMNITY**

University of Birmingham employees are indemnified by the University insurers for negligent harm caused by the design or co-ordination of the clinical trials they undertake whilst in the University's employment.

In terms of liability at a site, NHS Trust and non-Trust hospitals have a duty to care for patients treated, whether or not the patient is taking part in a clinical trial. Compensation is therefore available via NHS indemnity in the event of clinical negligence having been proven.

The University of Birmingham cannot offer indemnity for non-negligent harm. The University of Birmingham is independent of any pharmaceutical company, and as such it is not covered by the Association of the British Pharmaceutical Industry (ABPI) guidelines for patient compensation.

# **17. PUBLICATION POLICY**

Results of this trial will be submitted for publication in a peer reviewed journal. The manuscript will be prepared by the TMG and authorship will be determined by mutual agreement.

Any secondary publications and presentations prepared by Investigators must be reviewed by the TMG. Manuscripts must be submitted to the TMG in a timely fashion and in advance of being submitted for publication, to allow time for review and resolution of any outstanding issues. Authors must acknowledge that the trial was performed with the support of University of Birmingham. Intellectual property rights will be addressed in the Clinical Study Site Agreement between Sponsor and site.

